7.2 Patient Discontinuation/Withdrawal from the Study

A patient may withdraw from the study at any time at his/her own request, may permanently discontinue study medication but wish to remain in the study, or may be withdrawn from administration of study medication or from all study participation at the discretion of the Investigator at any time for safety, behavioral, compliance, or administrative reasons.

Withdrawn patients may need to be replaced, depending on the actual discontinuation rate.

See the SoA ([Section 1.3](#)) for data to be collected at the time of study discontinuation and follow-up and for any further evaluations that need to be completed.

- If the patient withdraws consent for disclosure of future information, the Sponsor may retain and continue to use any data collected before such a withdrawal of consent.
- If a patient withdraws from the study, he/she may request destruction of any samples taken and not tested, and the Investigator must document this in the study center study records.

7.3 Lost to Follow-up

- A patient will be considered lost to follow-up if he or she is unable to be contacted by the study center.
- Before a patient is deemed lost to follow-up, the Investigator or designee must make every effort to regain contact with the patient. These contact attempts should be documented in the patient's medical record.
- Should the patient continue to be unreachable, a telephone call to medical contacts listed in medical record will be performed to determine vital status. If dead – marked as death and date recorded. If unreachable, a vital records check may be conducted to determine if a death has occurred approximately 60 days following the 1st dose of study medication.
- If no death record is found and the patient or medical contact continues to be unreachable approximately 60 days following the 1st dose of study medication, he/she will be considered to have been lost to follow-up and withdrawn from the study.

7.4 Termination of the Study

Given the potential severity of COVID-19 and limited information about the expected clinical course, there are no pre-specified study stopping rules. Instead there will be close oversight by the protocol team composed of the Sponsor's Medical Monitor, the Investigator and 2 independent physicians, and frequent reviews of the safety data ([Section 11](#)).

Conditions that may warrant termination of the study include, but are not limited to:

- The discovery of an unexpected, serious, or unacceptable risk to patients enrolled in the study;
- The decision on the part of the Sponsor to suspend or discontinue testing, evaluation, or development of ensifentrine;
- Serious failure of the Investigator to comply with the International Council on Harmonization (ICH) Guidelines on Good Clinical Practice (GCP) or local regulations;
- Submission of knowingly false information from the research facility to the Sponsor, the Independent Ethics Committee (IEC) or any national regulatory officials;
- Major, repeated, non-adherence to the protocol.

The Sponsor must be informed immediately in the event of any major protocol deviation or serious breach of ICH GCP.

Study termination and follow-up will be performed in compliance with the conditions set forth in ICH GCP. The decision to discontinue the study is at the discretion of the Sponsor, the Investigator, the regulatory authority or IEC and should if possible be taken by mutual agreement. A record of such a discussion will be prepared and stored in the study file. The Sponsor will ensure the regulatory authorities and IECs are notified.

8 STUDY ASSESSMENTS AND PROCEDURES

- The SoA is in [Section 1.3](#).
- Protocol amendments, waivers or exemptions are discussed in [Section 9](#). Regulatory, ethical and study oversight details are included in [Appendix 2](#).
- Safety concerns related to use of the study medication should be discussed with the Sponsor immediately upon occurrence or awareness to determine if the patient should continue or discontinue study medication. The Investigator may discontinue study medication for a patient if deemed necessary. The treatment of any given subject may be stopped for SAEs, clinically significant adverse events, severe laboratory abnormalities, or any other medical conditions that indicate to the Investigator that continued dosing is not in the best interest of the patient. In addition, a subject in this clinical study may discontinue study drug at their request for any reason.
- Adherence to the study design requirements, including those specified in the SoA, is essential and required for study conduct as well as compliance discussed in [Section 9](#) and [Appendix 2](#) and regulatory requirements included in [Appendix 2](#).
- All screening evaluations must be completed and reviewed to confirm that potential patients meet all eligibility criteria. The Investigator will maintain a screening log to record details of all patients screened and to confirm eligibility or record reasons for screening failure, as applicable.
- Procedures conducted as part of the patient's routine clinical management (e.g., blood count) and obtained before signing of the ICF may be utilized for screening or baseline purposes provided the procedures met the protocol-specified criteria and were performed within the time frame defined in the SoA.
- The maximum amount of blood collected for study related procedures from each patient, will not exceed 500 mL. Repeat or unscheduled samples may be taken for safety reasons or for technical issues with the samples.
- Should a death occur in a study patient, data should be collected on whether the death occurred after withdrawal study medication and, if so, the reason for study drug withdrawal. Withdrawal of care, comfort care, do not resuscitate (DNR) orders will be captured in the event of a death.
- The site will attempt to follow-up on clinical status, but at a minimum the vital status of patients that do not have a telephone follow-up approximately 60 days following randomization and at least one dose of study medication.
- See [Section 5.3](#) for specific information to be collected for screen failures.

8.1 Collection of Data

Patients will be assessed daily while hospitalized. Clinical data will be recorded using eCRFs adapted from the WHO-ISARIC (World Health Organization–International Severe Acute Respiratory and Emerging Infections Consortium) case record form (<https://isaric.tghn.org>).

Screening and baseline information will be collected and recorded on the eCRF. This will include the following information:

- Informed consent review, eligibility review, including screening liver, kidney and pregnancy (if applicable) laboratory tests, and categorization of their positive COVID-19 disease severity (according to the FDA’s document: COVID-19: Developing Drugs and Biological Products for Treatment or Prevention Guidance for Industry, May 2020). Refer to [Section 8.1.2](#) for severity definitions.
- Demographics, hospital admission date (for COVID-19 infection), medical and smoking history, standard of care medications and treatments and type of facility transferred from.
- Existing co-morbidities and any medication taken for those listed as well as medications taken since admission.

Randomization information will be recorded on an eCRF. If study medication is dispensed, it will be recorded on this form.

Starting on Day 1 to discharge, Day 29 or withdrawal of consent, site staff will record on an eCRF daily the following information:

- Clinical status (7-point ordinal scale) each morning ([Section 8.1.1](#)).
- Vital signs each morning at approximately the same time ([Section 8.1.3](#)).
- Concomitant medications taken as part of SoC for COVID-19 infection treatment ([Section 6.5.1](#) and [Section 8.1.4](#)).
- Supportive treatments received as part of SoC for COVID-19 infection treatment or new infection that develops while hospitalized ([Section 8.1.4](#)).
- Routine laboratory, infection and imaging test results received as part of SoC ([Section 8.1.4](#)).
- Study medication doses taken and when.
- On the day of discharge or Day 29, safety laboratory tests may be performed at the discretion of the treating physician and, if completed, may be completed within 24 hours of the patient’s discharge from the hospital.
- Adverse events.

At discharge site staff will schedule a follow-up and complete an eCRF page including the following:

- Date of discharge and reason (e.g., COVID-19 negative, improved enough for discharge, etc.)
- Where the patient was discharged to (e.g., home, rehab center, etc.)
- If the patient was COVID-19 positive or negative at discharge (yes/no/unknown)
- Which medications the patient was discharged with
- If supplemental oxygen or other supportive treatment was prescribed for treatment after discharge

At the follow-up calls, site staff will complete eCRF pages including the following:

- Date of follow-up

- How patient is doing, their clinical (7-point ordinal scale) or minimally recording their vital status.
- Whether the patient had been re-hospitalized following discharge.
- Any adverse events or pregnancy
- A disposition eCRF for how the patient completed or did not complete (with reason) the study.

8.1.1 7-point ordinal scale of clinical improvement

Clinical status will be assessed using a 7-point ordinal scale. The ordinal scale is an assessment of the clinical status at the first assessment of a given study day. Each day, the worse score for the previous day will be recorded (i.e., on Day 3, Day 2 score is obtained and recorded as Day 2). The ordinal scale is adapted from the WHO R&D Blueprint expert group which measures illness severity over time (https://www.who.int/blueprint/priority-diseases/key-action/COVID19_Treatment_Trial_Design_Master_Protocol_synopsis_Final_18022020.pdf). The scale is listed in **Table 10**.

Table 10. 7-point ordinal scale.

1	not hospitalized, no limitations of activities
2	not hospitalized, limitation of activities, home oxygen requirement, or both
3	hospitalized, not requiring supplemental oxygen but requiring ongoing medical care
4	hospitalized, requiring any supplemental oxygen
5	hospitalized, requiring non-invasive ventilation or use of high-flow oxygen devices
6	hospitalized, receiving invasive mechanical ventilation or extracorporeal membrane oxygenation (ECMO); and
7	death

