Follow-up vital status				X	X	X		X	X	X
Re-hospitalization/Still in hospital status				X	X	X		X	X	X
Vital records search, if needed						X				X
[†]	Day 1 may take place on the same day as the screening/baseline visit, if appropriate. If Day 1 activities take place on the same day as screening/baseline visit, only 1 ordinal scale assessment and vital sign assessment are necessary, but they must be completed prior to dosing.									
[‡]	Discharge Contact: contact with the patient will take place 4 to 10 days after discharge from hospital within the 29-day treatment period. If the patient remains hospitalized after Day 29, contact with the patient will take place 4 to 10 days after receipt of last dose of study medication on Day 29.									
^{**}	Day 29 Contact (if patient discharged prior to Day 29): contact with the patient will take place 26 to 32 days after first dose of study medication. If the Discharge Contact and Day 29 Contact fall within same window, this contact will be combined as the Day 29 Contact.									
^{***}	Day 60 Follow-up: contact with the patient will take place 55 to 65 days after first dose of study medication.									
[*]	Record the physical exam documented by the treating team on the day of screening, and verify key parts (heart, lung).									
^Ω	If kidney (creatinine), liver (alanine aminotransferase or aspartate aminotransferase) and pregnancy (if applicable, via serum) were not run prior, they are required during the screening process. Refer to exclusion criteria in Section 5.2 and Appendix 3 .									
^β	Discharge safety laboratory tests may be completed at the discretion of the treating physician and, if completed, may be completed within 24 hours of the patient’s discharge from the hospital.									
[¥]	Vital signs should be recorded each morning at approximately the same time of a given study day. Variables: Respiration rate (per minute), Oxygen saturation (SpO2), Any supplemental oxygen (yes/no), Body temperature, Systolic blood pressure, Heart rate (pulse rate per minute); and Level of consciousness graded on the AVPU scale (Alert, Verbal = voice response present, Pain = pain response present, Unresponsive). Refer to Section 8.1.3 .									
¹	These assessments are not required to be completed prior to morning blinded study medication dosing.									

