^β	Ordinal scale clinical improvement assessed and recorded each morning at approximately the same time. The categories are as follows: 1=not hospitalized, no limitations of activities; 2=not hospitalized, limitation of activities, home oxygen requirement, or both; 3=hospitalized, not requiring supplemental oxygen but requiring ongoing medical care; 4=hospitalized, requiring any supplemental oxygen; 5=hospitalized, requiring non-invasive ventilation or use of high-flow oxygen devices; 6=hospitalized, receiving invasive mechanical ventilation or extracorporeal membrane oxygenation (ECMO); and 7=death. Refer to Section 8.1.1 .									
^Λ	Laboratory results performed as recommended by UAB treating physician: Record daily (or as performed) WBC, neutrophil count, lymphocyte count, creatinine values. Record every 2-3 days (or as performed) a) Inflammatory markers and b) LFTs. Those recommended for UAB staff include: BMP, CBC w/ diff, LFT, IL-6, ferritin, D-dimer every three days. See Section 8.1.4 and Appendix 3 .									
^Σ	Study staff, nursing and/or respiratory therapy to administer. The person administering and observing cannot be the unblinded pharmacist.									
²	Blinded study medication may be dosed as deemed appropriate by Investigator on day of discharge.									

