8.4 Discharge Activities

For the Day of Discharge (Day 29 or the last day in the hospital if discharged before Day 29), the Daily eCRF will be completed as above (**Table 13**) as well as a Discharge eCRF to document how the patient was discharged (**Table 14**).

Table 14. Day of discharge activities.

Assessment	Information
Record discharge information	
 • Discharged (yes/no).* • If discharged, the Date of discharge and reason (e.g., COVID-19 negative, recovered, not discharged [remains hospitalized] etc.) is noted. Date of scheduled follow-up telephone call. • Where the patient was discharged to (e.g., home, rehab center, etc.). • If the patient was COVID-19 positive or negative at discharge (yes/no/unknown). • Which medications the patient was discharged with. • If supplemental oxygen was prescribed for treatment after discharge.

* Patients not discharged from the hospital by Day 29

Some study patients may not be ready for discharge from the hospital by Day 29. In these instances, study treatment and data collection procedures still end on Day 29 (with the exception of contacts in the next section). This information will be noted in the Discharge eCRF as “study treatment complete, but patient remains hospitalized.” This would also be captured in the Day 29 Clinical status assessment (7-point ordinal scale).

Patients that remain hospitalized after Day 29 will be contacted as described in the next section.

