8.5 Post Discharge/Day 29 Contacts

Following Day 29 or discharge from the hospital (if earlier), there will be three points of contact with all study patients, regardless of hospitalization status. Each contact will require the completion of a Follow-up eCRF (**Table 15**).

- Discharge Contact: 4 to 10 days after discharge from hospital, if discharged within the 29-day treatment period.
 - If the patient remains hospitalized after Day 29, study treatment and data collection procedures still end on Day 29 (with the exception of contacts in this section) and contact with the patient will take place 4 to 10 days after receipt of last dose of study medication (Day 29).
- Day 29 Contact: 26 to 32 days after first dose of study medication. If the Discharge Contact and Day 29 Contact fall within same window, this contact will be combined to the Day 29.

- Day 60 Follow-up: 55 to 65 days after first dose of study medication.
 - Should a patient or their medical contact be unable to be contacted at any of these timepoints, a vital records search will be performed to determine the patient’s vital status approximately 60 days after first dose of study medication.

Table 15. Post-discharge follow-up activities.

Assessment	Information
Follow-up date	
 • Date of follow-up contact
Clinical status assessment (7-point ordinal scale)	
 • Assessed and documented, as above for Day 1 (clinical and vital status)
Re-hospitalization status or remains in hospital	
 • Any incidence of re-admission to the hospital following a 24-hour period of discharge (date and duration) that is related to COVID-19 • Date of discharge (if after Day 29) should be noted in the Follow-up eCRF.
Adverse Events assessments	
 • Documented, as above for Day 1

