Discharge	The patient is discharged and leaves the hospital alive. This does not include if a patient is moved to another unit.
	The time to discharge = the elapsed time (in days) from Day 1 to the earliest day at which the patient is Discharged from hospital (= Day where the 7-point ordinal scale score is equal to 1 or 2).
Improvement in	A decrease from baseline of at least one point in the 7-point ordinal score (eg, 5
clinical status	to 4).
Worsening	An increase from baseline of at least one point in the 7-point ordinal scale score
clinical status	(eg, 5 to 6).

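### Protocol 8.1.1 gives two conflicting rules for the daily ordinal score; separately, neither document fixes recovery day as the discharge date, so time to recovery is 4–10 days late if programmed from recorded scores

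*Protocol*

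**What the plan says.** **Scoring rule.** Protocol 8.1.1 defines the score twice in consecutive sentences. The first reads "The ordinal scale is an assessment of the clinical status at the first assessment of a given study day". The second reads "Each day, the worse score for the previous day will be recorded", with an example in which the score gathered on Day 3 is dated Day 2. The Schedule of Activities has only the morning version: "Ordinal scale clinical improvement assessed and recorded each morning at approximately the same time". Protocol 8.1 and Tables 11–13 also follow the morning or first assessment. SAP Table 4 refers back to Protocol 8.1.1 and does not choose. Baseline in SAP Table 4 is the last single reading before the first dose.

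**When scores exist.** Protocol 8.1: "Starting on Day 1 to discharge, Day 29 or withdrawal of consent, site staff will record on an eCRF daily the following information". Protocol 8.4: "For the Day of Discharge (Day 29 or the last day in the hospital if discharged before Day 29), the Daily eCRF will be completed". The next scheduled score is in Protocol 8.5: "Discharge Contact: 4 to 10 days after discharge from hospital, if discharged within the 29-day treatment period". The Schedule of Activities adds: "If the Discharge Contact and Day 29 Contact fall within same window, this contact will be combined as the Day 29 Contact".

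**How recovery is derived.** SAP Table 4 counts time to discharge up to the earliest day on which the patient is "Discharged from hospital (= Day where the 7-point ordinal scale score is equal to 1 or 2". SAP Table 5 assesses recovery with the ordinal score and ends time to recovery on the first day the patient satisfies category 1 or 2. SAP 8.5 carries the last assessment forward when a time point has no data and, for total-time endpoints, assumes unchanged status up to Day 29. The discharge date and any oxygen prescribed at discharge are recorded (Protocol 8.1 and Table 14). Neither document says that the discharge date is the recovery date.

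**The concern.** There are two separate defects in one instrument.

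1. A point-in-time score and a worst-of-day score are different measurements. A brief escalation counts under one and not the other. This matters for days on oxygen, days on non-invasive ventilation or high flow, new oxygen and new ventilation use, and change from baseline. Under the worst-of-day rule, a single pre-dose reading would be compared with later daily maxima.

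2. Scores 1 and 2 both require that the patient is out of hospital. A patient who starts the day as an inpatient cannot score 1 or 2 that day under either rule, and no score is scheduled until the Discharge Contact. The day SAP Table 4 identifies with discharge is therefore not the day on which a 1 or 2 first appears in the data. Two programmers could follow the SAP in good faith and differ by 4 to 10 days per patient on time to recovery.

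**Working it through.** **Step 1. The two rules side by side.**

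| Course within one day | First assessment | Worst of day |
|---|---|---|
| Room air in the morning, oxygen in the afternoon | 3 | 4 |
| Low-flow oxygen in the morning, high flow later | 4 | 5 |
| Inpatient in the morning, discharged alive later | 3 or more | 3 or more |

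The first two rows show the conflict. The third shows that neither rule marks recovery on the discharge day.

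**Step 2. Contact windows.** The Schedule of Activities gives 7 ± 3 days for the Discharge Contact: 7 − 3 = 4 and 7 + 3 = 10, which agrees with Protocol 8.5. The Day 29 Contact is 29 ± 3, so 26 to 32.

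**Step 3. Lag from discharge on day d to the first recorded 1 or 2.**
- Discharge date used as recovery day: lag 0.
- Recorded scores, contact on time: d + 4 to d + 10. Discharge on Day 10 gives Days 14–20.
- Contact merged into a late Day 29 Contact: discharge on Day 16, scored on Day 32, lag 32 − 16 = 16. If the window is counted as days after first dose (Days 27–33), the worst case is 33 − 17 = 16.
- Discharge Contact missed after discharge on Day 4: 26 − 4 = 22 up to 33 − 4 = 29 days.

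**Step 4. Day 7 and Day 14 endpoints.** No post-discharge score exists by target day T if d + 4 > T, and may not exist if d + 10 > T.
- T = 14: discharges on Days 11–14 have none; discharges on Days 5–10 may have none.
- T = 7: discharges on Days 4–7 have none.

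The analysis windows in Protocol 10.1 soften these limits by a day or two. Otherwise the SAP 8.5 carry-forward, read literally, gives these patients their last inpatient score, which counts as not recovered.

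**Step 5. Oxygen days.** A patient last scored 4 on the discharge morning has 4 − 1 = 3 to 10 − 1 = 9 unscored days before an on-time contact. Unchanged-status imputation would count them as oxygen days even if the patient went home without oxygen.

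**Step 6. Illustration of the effect on time to recovery.** The plan states no power figure to reproduce. Assumptions: 30 versus 15 patients, Weibull times to discharge (shape 1.8), no deaths, a uniform 4–10 day lag, log-rank test at two-sided 5%, 2,000 replicates. Medians of 10 and 13 days are the range of hospital stay cited in Protocol 4.3; 7 is assumed. Each cell gives discharge date → recorded scores.

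| Assumed median | Control median, HR 1.0 | Recovered by Day 29, HR 1.0 | Power, HR 2.0 |
|---|---|---|---|
| 7 | 7.6 → 14.7 | 100% → 99% | 57% → 47% |
| 10 | 10.6 → 17.6 | 99% → 94% | 53% → 49% |
| 13 | 13.6 → 20.7 | 95% → 83% | 56% → 50% |

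The median moves by about 7 days, which is the mean lag (4 + 10)/2. Rejection under HR 1.0 stays at about 5–7% either way. The recovered column uses Discharge Contact scores only, so it describes events in the time-to-recovery analysis and not the primary endpoint.

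**The case against.** The best defence is that the plan can be read as dating recovery at discharge. SAP Table 4 defines discharge as leaving hospital alive and puts the event first, with the score as a gloss. SAP Table 5 and Protocol 3.2.1 speak of the day a category is satisfied, not the day a score is recorded, and live discharge satisfies category 1 or 2 by definition. The discharge date is collected. The shell for Table 14.2.5 runs to Day 29 or discharge, whichever is first. SAP 8.5 adds no hospital days after discharge when no further hospitalization data exist. All of this stands: the delay is conditional on programming. What remains is that SAP Table 4 equates two days that differ in the recorded data, and that SAP 8.5 has no rule for recovery or oxygen status in the unscored days, only one for hospital days.

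A reader might infer four stronger things that the documents do not support.
- *That the plan does date recovery at the contact for most patients.* No section says so.
- *That the delay follows from the conflict between the rules.* It comes from the absence of scoring after discharge and would remain whichever rule were kept.
- *That the whole 4–10 days is noise comparable to the hospital stay.* Most of it is a shift applied to both blinded arms. With on-time contacts the variable part is about ±3 days, and apart from truncation at Day 29 a common shift leaves the log-rank ordering unchanged.
- *That every efficacy endpoint is affected.* Re-hospitalization comes from an eCRF question and death may come from vital records. The Day 29 primary proportion is largely protected because status is obtained at the Day 29 Contact.

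The trial is also exploratory and unpowered, so the loss of power in the illustration is not a failure of a stated design property.

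**Conclusion.** Both defects hold, and neither depends on the other. The scoring conflict is explicit, and its effect is limited to endpoints that count or compare daily scores; its size cannot be given without knowing how often status changes within a day. The recovery-day gap is an ambiguity: lag 0 if the discharge date is used, 4–10 days if recorded scores are used with on-time contact, and longer if contacts are merged or missed. The chief consequences are a time-to-recovery estimate about a week too long in both arms, possible misclassification at Days 7 and 14, and possible extra oxygen days. Under the assumed distributions, the cost in power at HR 2.0 is about 4 to 10 percentage points. The illustration rests on those assumptions and on no document figure beyond the contact window, the 30:15 allocation, the 5% level and the cited length of stay. Because the choice is worth several days per patient in a small trial read for trends across endpoints, it should be settled before unblinding.

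**What to change.** 1. Keep one scoring rule and apply it in Protocol 8.1.1, the Schedule of Activities, Protocol 8.1, Tables 11–13 and SAP Table 4. The first (morning) assessment already matches most of the text and the single-reading baseline. A worst-of-day rule would require rewriting those sections and would sit awkwardly with a score of 1 or 2 on the discharge date.

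2. In SAP Tables 4 and 5 and SAP 8.5, state that recovery day is the date of live discharge on the Discharge eCRF. Recovered status (1 or 2) is held from that date until the next contact or readmission and overrides carry-forward of the last inpatient score. Use the recorded discharge oxygen to decide home-oxygen days.

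3. Say in the same place whether the discharge day itself counts as a hospital day and an oxygen day, since the morning score and the derived status will differ on that day.

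The cost is wording only. The discharge date and discharge oxygen are already collected, and no new assessment is needed. If scores have already been collected, the SAP should also record which rule the site actually used.
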